9.1.3.5. Work Productivity and Activity Impairment Questionnaire–Spondyloarthritis

The WPAI-SpA consists of 6 questions to determine employment status, hours missed from work because of SpA, hours missed from work for other reasons, hours actually worked, the degree to which SpA affected work productivity while at work, and the degree to which SpA affected activities outside of work. The WPAI-SpA has been validated in the r-axSpA patient population (Reilly et al. 2010). Four scores are derived: percentage of absenteeism, percentage of presenteeism (reduced productivity while at work), an overall work impairment score that combines absenteeism and presenteeism, and percentage of impairment in activities performed outside of work. Greater scores indicate greater impairment (Reilly Associates [WWW]).

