6.1. General Considerations

Statistical analysis of this study will be the responsibility of Eli Lilly and Company (hereafter Lilly). The statistical analyses will be performed using SAS® Version 9.4 or higher.

Continuous data will be summarized in terms of the number of observations, mean, standard deviation (SD), minimum, median, and maximum. The minimum and maximum will be reported to the same number of decimal places as the raw data recorded in the database. The mean and median will be reported to 1 more decimal place than the raw data recorded in the database. The SD will be reported to 2 more decimal places than the raw data recorded in the database. In general, the maximum number of decimal places reported shall be 4 for any summary statistic.

Categorical data will be summarized in terms of the number of patients in the analysis population, the number of patients providing data at the relevant time point, frequency counts, and the percentages corresponding to the appropriate method. Percentages will be presented to 1 decimal place. Percentages will not be presented for zero counts.

For continuous data, at visits of interest, change from baseline will be calculated as the observed value - the baseline value. Percent change (or percent improvement) is calculated as $100 \times \frac{\text{Baseline value} - \text{Observed value}}{\text{Baseline value}}$. If the baseline value or observed value is missing, the change from baseline and percent change (or percent improvement) from baseline will be missing.

All confidence intervals (CIs) and statistical tests will be 2-sided unless otherwise specified. P-values which are greater than or equal to 0.001, and less than or equal to 0.999, will be presented to 3 decimal places. All other p-values which are less than 0.001 will be presented as <0.001, while p-values greater than 0.999 will be presented as >0.999. Confidence intervals will be presented to 1 more decimal place than the raw data.

Age, sex, and race will be reported on all by-patient listings unless otherwise specified. Sex will be abbreviated as follows: female (F) and male (M). Race will be abbreviated as follows: Asian (AS).

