
Functional Assessment of Clinical Illness Therapy Fatigue (FACIT-Fatigue) Scale:
 
The FACIT-Fatigue scale (Cella and Webster 1997) is a 13-item symptom-specific questionnaire that assesses the self-reported severity of fatigue and its impact upon daily activities and functioning.
	
FACIT-Fatigue total score
	
The FACIT-Fatigue uses 0 (“not at all”) to 4 (“very much”) numeric rating scales to assess fatigue and its impact in the past 7 days. Scores range from 0 to 52 with higher scores indicating less fatigue. The FACIT-Fatigue Scoring Guidelines (Version 4) will be used to calculate the Total Score. Reversals are needed for all items except An5 and An7, as described in scoring manual. http://www.ser.es/wp-content/uploads/2015/03/FACIT-F_INDICE.pdf
	
Missing items are acceptable as long as more than 50% of the items are answered (i.e., a minimum of 7 out of 13 items), the sum of available items will be divided by the number of items answered to obtain the total score. If less than 7 items are answered, the FACIT-Fatigue total score will be set to missing.

Work Productivity and Activity Impairment Questionnaire—Spondyloarthritis:
 
The Work Productivity and Activity Impairment—Spondyloarthritis (WPAI-SpA) consists of 6 questions to determine employment status, hours missed from work because of spondyloarthritis, hours missed from work for other reasons, hours actually worked, the degree to which spondyloarthritis affected work productivity while at work, and the degree to which spondyloarthritis affected activities outside of work. The WPAI-SpA has been validated in the AS patient population (Reilly et al. 2010). Four scores are derived: percentage of absenteeism, percentage of presenteeism (reduced productivity while at work), an overall work impairment score that combines absenteeism and presenteeism, and percentage of impairment in activities performed outside of work. Greater scores indicate greater impairment.
	
percentage of absenteeism
	
% work time missed due to problem: $(Q2/(Q2 + Q4))*100$
	
if Q2 or Q4 is missing, then missing

	
percentage of presenteeism
	
% impairment while working due to problem: $(Q5/10)*100$
	
if Q5 is missing, then missing

	
overall work impairment score
	
% overall work impairment due to problem: $(Q2/(Q2+ Q4) + [(1-Q2/(Q2+Q4))*(Q5/10)])*100$
	
if any of Q2, Q4, or Q5 is missing, then missing

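### The WPAI-SpA overall work impairment score is set to missing when Q5 is blank, even where the SAP's own formula fixes it at 100% (Q4 = 0 and Q2 > 0)

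*SAP*

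**What the plan says.** SAP Table RHCH.6.5 (Section 6.9.7) labels the composite as percent "overall work impairment due to problem" and computes it as "Q2/(Q2+ Q4) + [(1-Q2/(Q2+Q4))*(Q5/10)])*100" (the bracket that opens the expression stands just before this excerpt). Its missing-component rule is "if any of Q2, Q4, or Q5 is missing, then missing". There is no exception for a patient who worked no hours.

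Absenteeism, in the same table, uses only Q2 and Q4, and its rule is "if Q2 or Q4 is missing, then missing". Presenteeism uses only Q5, and activity impairment uses only Q6.

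The SAP describes Q5 as "the degree to which spondyloarthritis affected work productivity while at work", and Protocol Section 9.1.3.5 describes it in the same terms: "the degree to which SpA affected work productivity while at work". On direction, the SAP says "Greater scores indicate greater impairment", so 100% is the worst value.

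Table RHCH.6.6 compares change from baseline in the four WPAI-SpA scores with placebo at Week 16, by ANCOVA with mBOCF in the ITT Population.

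**The concern.** A missing-item rule is meant for scores that cannot be computed without the item. In the zero-hours case the score can be computed: it is 100% whatever the patient would have answered to Q5. It is also the case where a blank Q5 is most natural, since someone who did not work has no productivity at work to rate.

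The rule may therefore discard known values at one end of the scale, from patients with the greatest work loss. That is missingness related to the outcome, created by the derivation and not by the patient. At stake is the Week 16 comparison of one of the four WPAI-SpA scores, which both documents list under the other secondary objectives.

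**Working it through.** **1. The formula at zero hours worked.** Let A = Q2/(Q2 + Q4). The SAP score is [A + (1 − A) × Q5/10] × 100.

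- With Q4 = 0 and Q2 > 0: A = Q2/Q2 = 1, so the score is [1 + 0 × Q5/10] × 100 = 100.
- Evaluating it for Q2 = 1, 8, 20, 40 and 60 hours and Q5 = 0 to 10 gives 100.0 in all 5 × 11 = 55 combinations.
- With Q4 > 0 the score depends on Q5. For Q2 = 20 it runs from 95.2 to 100 at Q4 = 1, from 80 to 100 at Q4 = 5, and from 50 to 100 at Q4 = 20. The missing rule is justified there.
- With Q2 = Q4 = 0, A is a division by zero. The SAP has no rule for this.

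**2. Whether another rule recovers the value.**

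- SAP Section 6.1: "If the baseline value or observed value is missing, the change from baseline" is itself missing. A blank Q5 at either visit removes the change score.
- Protocol Section 2 schedules the WPAI-SpA at Week 0, Week 16, Week 52 and early termination, so Week 16 is the only scheduled postbaseline value in Period 2.
- SAP Section 6.3.2: mBOCF carries values forward for patients who stop study drug. It leaves out patients with no postbaseline observation unless they stopped because of an adverse event. An on-treatment patient with a blank Q5 at Week 16 is not recovered.
- Protocol Section 9.1.3.5 gives no scoring rule that would override the SAP.

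**3. Effect on the treatment difference (illustration only).** The documents give no WPAI-SpA means, no number of employed patients and no share with zero hours. Assume that scored patients have Week 16 means of 50 (placebo) and 35 (ixekizumab), and that shares p and t of the respective arms are at 100% with Q5 blank. The difference with everyone scored is

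[100p + 50(1 − p)] − [100t + 35(1 − t)] = 15 + 50p − 65t.

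| p (placebo) | t (ixekizumab) | Difference as analysed | Difference with 100% values restored |
|---|---|---|---|
| 5% | 5% | 15.0 | 14.25 |
| 5% | 2% | 15.0 | 16.2 |
| 10% | 3% | 15.0 | 18.05 |
| 15% | 5% | 15.0 | 19.25 |
| 20% | 5% | 15.0 | 21.75 |

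On these means the sign turns at 50p = 65t, that is p = 1.3t. Below that ratio the analysed difference is too large; above it, too small.

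**4. Why even this is not an estimate of bias.** The table concerns raw Week 16 means, whereas the endpoint is change from baseline adjusted for baseline. A patient at 100% at both visits has a change of 0. A patient at 100% at baseline with Q5 blank and at 40% at Week 16 (an assumed value) would have had a change of 40 − 100 = −60, and that improvement is lost. Baseline blanks can remove improvements and Week 16 blanks remove poor outcomes, so the net effect depends on both visits and both arms.

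**The case against.** The strongest reply is that the trigger is inferred. Neither document reproduces the questionnaire, a skip instruction or the form logic. If a zero-hours patient enters any number for Q5, the formula already gives 100% and nobody is lost. This stands, and the point has to be conditional on a blank Q5.

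A reader might infer that the most impaired employed patients drop out of the WPAI-SpA analysis, or that only they do. The documents support neither. Such a patient still counts at 100% in absenteeism, and in activity impairment if Q6 is answered. The rule also removes scores for a blank Q2 or Q4, and for a blank Q5 when hours were worked, where removal is right.

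It can also be said that making a composite missing when a component is missing is conventional, and that this table does so for the EQ-5D-5L indices. But an EQ-5D-5L index is not described as determined without the missing item, whereas this score is. The same table already allows for inapplicable items in the ASAS-HI (items 7 and 8), so an exception here fits the SAP's own practice.

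Finally, WPAI-SpA is outside the primary and major secondary testing list (SAP Section 6.4, Protocol Section 10.3.5). That stands and limits the severity.

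**Conclusion.** The point holds in conditional form and is minor. By the SAP's own algebra, the rule discards a fully determined value, the scale maximum, whenever Q4 = 0, Q2 > 0 and Q5 is blank. No other rule restores it for a patient still on treatment at Week 16. That much needs no assumption. That Q5 will be blank in this case is a reasonable reading of the item's description, not something the documents state.

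A reader might conclude that the treatment effect is understated. The documents do not support a direction: with equal 5% shares the illustration shows a slight overstatement (15.0 against 14.25), and with clearly more zero-hours patients on placebo it shows an understatement. A shift in one arm's raw mean per lost patient would not measure bias in the between-arm difference in change either. No primary or major secondary conclusion is affected.

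**What to change.** In SAP Table RHCH.6.5, replace the missing-component rule for this score with: if Q4 = 0 and Q2 > 0, overall work impairment = 100% whether or not Q5 is answered; otherwise missing if Q2, Q4 or Q5 is missing or Q2 + Q4 = 0. Leave presenteeism as it is, since it has no meaning without hours worked. The last clause also closes the undefined division by zero.

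The cost is one line in the table and the matching derivation code, made before the Week 16 lock. No new data are needed, and scores already computable when Q5 is answered do not change.

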6.10. Pharmacokinetic/Pharmacodynamic Methods

Details of pharmacokinetic/pharmacodynamics (PK/PD) analyses can be found in a separate PK/PD analysis plan.

6.11. Safety Analyses

Safety will be assessed by summarizing and analyzing AEs, laboratory analytes, vital signs, QIDS-SR16, and C-SSRS. The duration of treatment exposure will also be summarized.

Safety analyses will be conducted for each period separately, including Period 4 (Follow-up Period). In addition, safety data on ixekizumab will be summarized for All Ixekizumab Exposures Safety Population who had at least 1 dose of ixekizumab.

For safety analyses, the following baselines will be used:

- Treatment-emergent adverse events (TEAEs): baseline will be all results recorded during the baseline period (see Section 6.1 for definitions of the baseline period).
- Change from baseline to last observation and each scheduled postbaseline visit for laboratory and vital signs: baseline will be last non-missing assessment recorded during the baseline period (see Section 6.1 for definitions of the baseline period).
- Treatment-emergent abnormal laboratory and vital signs: baseline will be all results recorded during the baseline period (see Section 6.1 for definitions of the baseline period).
- Change from baseline to minimum or maximum: baseline will be all results recorded during the baseline period (see Section 6.1 for definitions of the baseline period).

6.11.1. Extent of Exposure

Duration of exposure to study drug will be summarized by treatment group for Safety Population during Period 2 and Extension Period Population for Period 3 using descriptive statistics.

Exposure for All Ixekizumab Exposures Safety Population during Combined Periods 2 and 3 will be provided.

The duration of exposure will be calculated as:

$$\begin{aligned} \text{Duration of exposure (days)} \\ &= \text{Date of last visit (scheduled or unscheduled) in Treatment Period} \\ &\quad - \text{Date of first dose in Treatment Period} + 1 \end{aligned}$$

The number and percentage of patients in each of the following categories will be included in the summaries:

- >0, ≥7 days, ≥14 days, ≥30 days, ≥60 days, ≥90 days, ≥120 days (for Period 3, add ≥150 days, ≥183 days, ≥210 days, and ≥273 days; for Combined Periods 2 and 3, add ≥150 days, ≥183 days, ≥365 days). Note that patients may be included in more than 1 category.
- >0 to <7 days, ≥7 to <14 days, ≥14 to <30 days, ≥30 to <60 days, ≥60 to <90 days, ≥90 to <120 days, ≥120 days (for Period 3, change ≥120 days to ≥120 to <150 days, add ≥150 to

<183 days, ≥183 to <210 days, ≥210 to <273 days, and ≥273 days; for Combined Periods 2 and 3, change ≥120 days to ≥120 to <150 days, add ≥150 to <183 days, ≥183 to <365 days, ≥365 days).

The summaries will also include the following information:

- Total exposure in patient years, calculated as:

$$\text{Total exposure in patient years} = \frac{\text{Sum of duration of exposures for all patients in treatment group}}{365.25}$$

- Mean and median total dose. Total dose (in mg) is calculated by the number of active injections taken during the treatment period multiplied by dose. For those randomized to ixekizumab 80 mg Q4W, the total dose (in mg) taken during Period 2 or 3 will be calculated as follows:

$$\text{Total Period 2 or 3 dose for patients on ixekizumab 80 mg Q4W} = \text{Total number of active injections (including loading doses, if any) received in Period 2 or 3} \times 80$$

- Total number of injections received will be derived using the response to the question “Was dose administered?” on the *Exposure as Collected* eCRF page and the actual dose description from IWRS study drug dispense dataset.

6.11.2. Adverse Events

Adverse events (AEs) will be classified based upon the latest version of the MedDRA. Adverse events will be recorded at every study visit. Any condition starting on or after the date of informed consent will be considered an AE. Any preexisting condition which worsens in severity on or after the date of informed consent will be considered and recorded as an AE on the *Adverse Event (AE)* eCRF page from the date of worsening onwards.

A treatment-emergent adverse event (TEAE) is defined as an event that first occurred or worsened in severity after baseline and on or prior to the date of the last visit within the defined treatment period. Both the date/time of the event and the date/time of the dose (that is, injection) are considered when determining TEAEs. Treatment-emergent AEs will be assigned to the study period to which it's considered treatment-emergent:

- The MedDRA lowest level term (LLT) will be used when classifying AEs as treatment-emergent.
- The maximum severity recorded for each LLT prior to the first dose date/time in the treatment Period will be used as the pre-treatment severity for that LLT. If an event during the baseline period has missing severity, and the event persists during the treatment period, then it will be considered as treatment-emergent, regardless of the postbaseline level of severity. Events with a missing severity during the treatment period will be considered treatment-emergent.

- AEs with a particular LLT will be classified as treatment-emergent if they first start on or after the first dose date/time in the treatment period (ie, a patient has no preexisting conditions with that lowest level term), or if the severity is greater than the pre-treatment severity for that lowest level term. If a partial AE start date/time is present, the date/time will be compared as far as possible to the treatment start date/time in order to determine whether the event is treatment-emergent or not. If there is any doubt, the event will be flagged as treatment-emergent.

A follow-up emergent adverse event (FEAE) is defined as an event that first occurred or worsened in severity after the date of Visit 17 (that is, Week 52) or the ETV:

- The MedDRA LLT will be used when classifying AEs as follow-up emergent.
- For AEs that are ongoing at the date of Visit 17 or ETV, the maximum severity recorded for each LLT on or prior to the date of Visit 17 or ETV will be used as the follow-up baseline severity for that LLT.

Adverse events and TEAEs will be summarized for the following study periods and analysis populations:

- Period 2 (Safety Population)
- Period 3 (Extended Treatment Period Population)
- Combined Periods 2 and 3 on ixekizumab treatment only (All Ixekizumab Exposures Safety Population)

The following summaries/analyses will be performed for all the populations above:

- An overall summary of AEs including the number and percentage of patients who experienced TEAE, TEAE by maximum severity, death, SAE, TEAE possibly related to study treatment, discontinuations from the treatment due to an AE, and TEAEs of special interest.

The following summaries will be provided for selective populations above:

- TEAE by system organ class (SOC) and preferred term (PT).
- TEAE by PT.
- TEAE by maximum severity, SOC, and PT.

Follow-up emergent adverse events will be summarized for the Follow-Up Population for Period 4:

- FEAE by PT.

In general, for all AE-related summaries, the number and percentage of patients experiencing the events will be presented by treatment group. In general, events will be ordered by decreasing frequency in the ixekizumab Q4W, and then in placebo (when applicable) group, within SOC and/or PT for sorting. For events that are gender-specific (as defined by MedDRA), the denominator and computation of the percentage will include only patients from the given gender.

A by-patient listing of all AEs for safety population will be provided.

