10.3.8.1. Adverse Events

Adverse events are classified based upon the Medical Dictionary for Regulatory Activities (MedDRA). A treatment-emergent adverse event (TEAE) is defined as an event that first occurred or worsened in severity after baseline and on or prior to the date of the last visit within the treatment period. Both the date/time of the event onset and the date/time of the first study drug injection are considered when determining TEAEs. Treatment-emergent adverse events will be assigned to the treatment period in which they first occurred or worsened. A follow-up emergent adverse event (FEAE) is defined as an event that first occurred or worsened in severity after the date of Week 52 (Visit 17) or the ETV. For events that are gender specific, the denominator and computation of the percentage will include only patients from the given gender.

An overall summary of AEs will be provided for each of the treatment periods, including the number and percentage of patients who experienced TEAEs, TEAEs by maximum severity, deaths, SAEs, TEAEs related to study drug, discontinuations from the treatment due to an AE, and treatment-emergent AESIs. Treatment-emergent adverse events (all, by maximum severity,

and TEAEs possibly related to study drug by the investigator), SAEs including deaths, and AEs that lead to treatment discontinuation will be summarized and analyzed by MedDRA system organ class (SOC) and preferred term.

In addition to general safety parameters, safety information on specific topics of AESIs will also be presented. Potential AESIs will be identified by a standardized MedDRA query (SMQ) or a Lilly defined MedDRA preferred term listing.

Follow-up emergent adverse events, SAEs including deaths, and AEs that lead to study discontinuation will be summarized for Period 4.

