6.1.1. General Considerations for Analyses during the Blinded Treatment Dosing Period (Period 2)

Comparisons between ixekizumab regimen 80 mg Q4W and placebo will be performed for all analyses in Period 2.

Period 2 starts at the first injection of study treatment at Week 0 (Visit 2) and ends prior to the first injection of study treatment at Week 16 (Visit 8) or the ETV (between Weeks 0 and 16). If a patient has Visit 8 but does not receive injection at Week 16 (Visit 8), the last recorded time for Visit 8 is used as the end time for Period 2.

Baseline will be defined as the last available value before the first injection for efficacy, health outcome, and safety analyses. In most cases, this will be the measure recorded at Week 0 (Visit 2). For efficacy measures, if the patient does not take any injection, the last available value on or prior to randomization date will be used. Change from baseline will be calculated as the visit value of interest minus the baseline value. For safety analyses using a baseline period, the baseline period is defined as the time from Visit 1 to the date/time of the first injection.

The randomization to treatment groups is stratified by baseline CRP status (nonelevated versus elevated) and TNF inhibitors experience (experienced or naïve) as described in Section 5.2. Unless otherwise specified, the statistical analysis models will adjust for baseline CRP status, and prior TNF inhibitors experience(if applicable).

The primary analysis method for treatment comparisons of categorical efficacy and health outcomes variables at specific time points will be made using a logistic regression analysis with treatment, baseline CRP status, and TNF inhibitors experience (if applicable) in the model. The proportions, odds ratio and 95% confidence intervals (CIs) will be reported; treatment difference and 95% CIs will also be reported. Secondary analysis will be conducted using a Fisher's exact test. In the case when logistic regression model does not produce statistical results due to sparse data, Fisher's exact test will be used.

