6.7. Treatment Compliance

By-patient listings of randomization schedule for the ITT Population and study drug dispensed (include the CT Lot number) for the Safety Population will be provided.

Throughout treatment periods, randomized patients will record information in a Study Drug Administration Log (captured in the *Exposure as Collected* eCRF page), including the date, time, and anatomical location of administration of investigational product, syringe number, who administered the investigational product, and the reason if the investigational product was not fully administered.

Treatment compliance for each patient per period will be calculated as:

$$\text{Treatment compliance (\%)} = 100 \times \frac{\text{Total number of injections administered}}{\text{Total number of injections expected}}$$

- For patients who complete Period 2, the number of injections expected during Period 2 will be equal to 5 (2 injections at Week 0 and 1 injection every 4 weeks from Week 4 to Week 12).
- For patients who complete Period 3, the number of injections expected during Period 3 will be equal to 10 (2 injections at Week 16 and 1 injection every 4 weeks from Week 20 to Week 48).
- For patients who discontinue during the treatment period, the number of injections expected during that period can be derived by considering the IWRS study drug dispense dataset and the treatment disposition date.
- The total number of injections administered will be derived using the response to the question “Was dose administered?” on the *Exposure as Collected* eCRF page.

A patient will be considered overall compliant with study treatment within each treatment period if he/she misses no more than 20% of the expected doses, does not miss 2 consecutive doses (all injections at an injection week are counted as 1 dose), and does not over-dose (that is, take more injections at the same time point than specified in the protocol).

Patient treatment compliance by treatment week and overall will be summarized for the Safety Population for Period 2 and for the Extended Treatment Period Population for Period 3.

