6.11.3. Deaths, Other Serious Adverse Events, and Other Notable Adverse Events

By-patient listings of deaths, SAEs, and AEs leading to discontinuation will be provided, respectively.

All deaths will be included, regardless of the investigator's or the sponsor's judgment about causality, including:

- any deaths occurring during participation in the study in the database for which data are being presented
- any deaths occurring after a patient leaves (is discontinued from or completed) the study in the database for which data are being presented if the death is:
 - the result of a process initiated during the study, regardless of when it actually occurred, or
 - occurs during the Period 4 after discontinuation of study drug.

An SAE is any AE that results in one of the following outcomes: death, life-threatening, initial or prolonged hospitalization, disability or permanent damage, congenital anomaly or birth defect, or any other serious/important medical events.

The following summary tables will be provided for the Safety Population for Period 2, and for the Extended Treatment Period Population for Period 3, as well as Combined Periods 2 and 3 for All Ixekizumab Exposures Safety Population:

- SAEs by PT
- AEs that lead to treatment discontinuation (including death) by PT.

A follow-up emergent serious adverse event (FESAE) is defined as an SAE that first occurred or worsened in severity after the date of Visit 17 (that is, Week 52) or the ETV. The following summary tables will be provided for the Follow-Up Population for Period 4:

- FESAE by PT

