Major Adverse Cerebro-Cardiovascular Events (MACE)	
MACE (requiring adjudication as defined above) is defined as:
 
 • Vascular Death (including cardiovascular and cerebro-vascular causes excluding hemorrhagic deaths outside of the central nervous system) • Non-fatal myocardial infarction • Non-fatal stroke (subtypes: hemorrhagic stroke, ischemic stroke, undetermined stroke type) 
Where,
 
 • Vascular death should be captured as an Event on Adjudication - Death eCRF page with Adjudication Death Type = 'Cardiovascular'. • Non-fatal myocardial infarction should be captured as an Event on Adjudication - Cardiac Ischemic Event eCRF page with Type of Ischemic Event = "Myocardial Infarction" and the Event is NOT on Adjudication - Death eCRF page. • Non-fatal strokes (ischemic, hemorrhagic) should be captured as an Event on Adjudication - Cerebrovascular Event eCRF page with Stroke Cerebrovascular Event Subtype in one of the following categories: hemorrhagic stroke, ischemic stroke, undetermined stroke type, and the Event is NOT on Adjudication - Death eCRF page. Subcategories of non-fatal stroke (Hemorrhagic Stroke, Ischemic Stroke, and Undetermined Stroke Type) will be displayed nested within non-fatal stroke category. 	
Period 2 (Fisher's exact test), Period 3 and Combined Periods 2 and 3 (Summary): TEAE by maximum severity by PT within category
 
Listing: TEAE

Malignancies	
Malignancy is defined using PTs from the Malignant or unspecified tumors SMQ as specified in MedDRA (SMQ: 20000091, which includes the sub-SMQs:
 
 • 20000194 [Malignant tumours], including sub-SMQs of 20000227 [Haematological malignant tumours] and 20000228 [Non-haematological malignant tumours] • 20000195 [Tumours of unspecified malignancy], including sub-SMQs of 20000229 [Haematological tumours of unspecified malignancy] and 20000230 [Non-haematological tumours of unspecified malignancy] 	
Period 2 (Fisher's exact test), Period 3 and Combined Periods 2 and 3 (Summary): TEAE by PT within category
 
Listing: TEAE

Special Safety Topic	Definition / Derivation	Analysis / Summary / Listing

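### An adverse event that starts after a patient's last visit, when there is neither an ETV nor a Week 52 visit, is neither treatment-emergent nor follow-up-emergent

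*SAP*

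**What the plan says.** SAP 6.11.2 gives the TEAE window an upper limit: the event must have "first occurred or worsened in severity after baseline and on or prior to the date of the last visit within the defined treatment period". Protocol 10.3.8.1 has the same limit, "on or prior to the date of the last visit within the treatment period".

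The follow-up window has one kind of starting point. An FEAE is "an event that first occurred or worsened in severity after the date of Visit 17 (that is, Week 52) or the ETV". SAP 6.11.3 repeats this for serious events: "an SAE that first occurred or worsened in severity after the date of Visit 17 (that is, Week 52) or the ETV". The Follow-Up Population (SAP 6.1.5) contains only patients who have entered Period 4, and Protocol 5.1 sends patients who discontinue early through the ETV to get there.

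Two other passages define a TEAE with no upper limit: the bullet in SAP 6.11.2 that classifies events by their onset relative to first dose, and the TEAE entry in Protocol Appendix 1.

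Some special-topic outputs in SAP Table RHCH.6.7 are specified in terms of TEAEs. For MACE the output is "TEAE by maximum severity by PT within category".

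**The concern.** The two windows meet only if the patient attends an ETV or the Week 52 visit. Without either, the first window closes at the last visit and the second never opens. An event that itself prevents the next visit falls after the last visit by construction, so the loss can depend on the outcome. At stake is whether a table of TEAEs, or of a special topic such as malignancy, contains every event known to have started on treatment. A report could show a cardiovascular death among the deaths and SAEs and none in its MACE table.

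**Working it through.** No figure in the plan has to be reproduced; this is a check of definitions.

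**Rules as written.** Let T be the onset day, L the day of the last visit in the treatment period, and E the day of the ETV or Week 52 visit, if there was one.

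- TEAE: first dose ≤ T ≤ L (SAP 6.11.2; Protocol 10.3.8.1).
- FEAE: T > E (SAP 6.11.2). If E does not exist, this cannot be met.

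**Illustrative cases (first dose on day 0).**

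| Case | T | L | E | TEAE | FEAE |
|---|---|---|---|---|---|
| Event before an attended ETV | 70 | 75 | 75 | yes | no |
| Event after an attended ETV | 80 | 75 | 75 | no | yes |
| Death between visits | 70 | 56 | none | no | no |
| Event known to the site, patient never returns | 60 | 56 | none | no | no |
| Event before the last visit, no ETV | 50 | 56 | none | yes | no |

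Only the third and fourth cases fall through.

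**Does last visit mean an actual visit?** Yes. SAP 6.11.1 ends exposure at the last visit, scheduled or unscheduled. The infection-duration rule in Table RHCH.6.7 names the last visit and the date of early discontinuation as separate end dates. It uses the second only for infection duration.

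**Is there a fallback?** None was found. SAP 6.1.1 covers a Visit 8 without an injection but not a missing ETV. The instruction in SAP 6.11.2 to flag doubtful cases as treatment-emergent concerns partial start dates compared with treatment start, so it does not extend the upper limit.

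**Length of the gap.** From Week 4 the Schedule of Activities has visits 28 days apart. Allowing for visit windows, Visit 5 (day 28 ± 2) to Visit 6 (day 56 ± 4) can span 60 − 26 = 34 days, and later pairs, such as day 56 ± 4 to day 84 ± 4, can span 88 − 52 = 36 days. An event can thus start about five weeks after the last visit before the next visit is overdue.

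**Where the event still appears.** These outputs are not limited to TEAEs:

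- the death, SAE and discontinuation-due-to-AE counts in the overall summary, and the by-patient listing of all AEs (SAP 6.11.2);
- the death and SAE listings, and the tables by preferred term of SAEs and of AEs leading to discontinuation (SAP 6.11.3);
- the registry SAE summary (SAP 6.15).

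**Where it does not.** It is absent from the TEAE tables in SAP 6.11.2 and from the special-topic outputs specified as TEAEs, such as malignancy, IBD and depression.

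**Where the SAP is ambiguous.** For cerebro-cardiovascular events the output column of Table RHCH.6.7 says TEAE, but the definition column says that every event qualifying for adjudication is used. MACE is likewise derived from the adjudication forms but output as TEAEs.

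**The case against.** The strongest reply is that little of consequence is lost. Fatal and hospitalising events are SAEs by definition, and deaths and SAEs are tabulated whether or not they are TEAEs. That stands. A reader might infer that fatal or incapacitating events on drug disappear from the safety report, or survive only in listings. The documents do not support that.

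Four further replies also stand:

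- Very few patients should qualify. Protocol 5.1 and 8.1.1 require an ETV after discontinuation, and a patient lost to follow-up under Protocol 8.3 cannot be contacted, so later events will seldom be known.
- Events on or before the last visit remain TEAEs. A later unscheduled visit within the period brings an earlier event back inside the window.
- Exposure also stops at the last visit, so events and person-time are cut at the same point. The rule is the same in both arms, and nothing in the documents shows that it distorts the Period 2 comparison.
- Exclusion from the cerebro-cardiovascular and MACE tables is one reading of conflicting columns, so it cannot be stated as certain.

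None of this puts a known non-serious event, or a between-visit malignancy or IBD event, back into the TEAE-based tables. Nor does it settle which TEAE wording governs.

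**Conclusion.** The gap is real and follows from the written definitions, but it is minor. It covers only events that start after the last visit, in patients with neither an ETV nor a Week 52 visit. For those events the loss from the TEAE tables is complete. For the adjudicated tables it depends on which column of Table RHCH.6.7 governs. No efficacy result is touched.

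The documents give no rate of leaving without an ETV. If 2% to 5% of 140 patients did so (an assumption), that would be 0.02 × 140 = 2.8 to 0.05 × 140 = 7, or about 3 to 7 patients. This counts patients, not lost events; an event is lost only if it also starts after the last visit and the site learns of it. A reader might infer that a MACE count would fall from one to zero. That needs both an expected MACE count, which the documents do not give, and the TEAE-only reading of the MACE table.

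**What to change.** 1. In SAP 6.11.2, for patients with neither the period-end visit (Visit 8 or Visit 17) nor an ETV, end the TEAE window at the later of the last visit and the treatment disposition date, or at the date of death.
2. Use the same end date for exposure in SAP 6.11.1, so that events and person-time stay aligned.
3. Bring the SAP 6.11.2 bullet and the headline definition into line, and say that the definition with an upper limit governs over the Protocol Appendix 1 entry.
4. In Table RHCH.6.7, state that all adjudicated events in that window enter the cerebro-cardiovascular and MACE tables.
5. Report the departure from Protocol 10.3.8.1, with its justification, in the CSR, as Protocol 10.3 requires for analysis changes that do not need an amendment.

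The cost is a few sentences and one derived date. The dates exist: Protocol 8.1 collects discontinuation dates for all randomized patients, SAP 6.5 lists them, and SAP 6.7 already says that expected injections "can be derived by considering the IWRS study drug dispense dataset and the treatment disposition date".

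There is a downside. For patients lost to follow-up, a late disposition date adds some unobserved person-time and could slightly dilute exposure-adjusted rates. An event that starts after the new end date would still have no window and would need to be read from the listings.
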